Several secondary outcomes relate to the safety of iron supplementation. To maximize the power to detect an association between group membership and safety outcomes a composite of SAEs, gastro-intestinal problems, malaria, and bacterial infections will be constructed and compared between the groups. The frequency of this composite will be compared between groups using Fisher's exact test. Furthermore, logistic regression models will be fit with group membership, sex, and age as covariates and the odds ratio associated with group membership will be estimated along with a 95% confidence interval. Components of the composite will also be investigated using a similar approach. The incidence of grade 3 or 4 AEs will be treated in a similar fashion. The frequency of responses to specific questions about known side effects to iron supplementation will be compared between the groups using logistic regression, controlling for sex and age. Each question will be investigated in addition to a response to any of the questions.

Since the treatment is not assigned at random there is a strong potential that confounders will introduce bias into the estimates of the treatment effects. As an attempt to remedy this, sensitivity analyses using inverse probability weighting will be conducted. If we use to represent group membership for participant i and Z_i is a vector of predictors for this participant, the first step of the analysis is to estimate the stabilized inverse probability of "treatment" weights W_i for subject i , $W_i = P(X_i = x_i)/P(X_i = x_i|Z_i)$. An estimate of $P(X_i = x_i|Z_i)$ can be obtained by logistic regression and $P(X_i = x_i)$ can be estimated by the sample proportion. One then uses these weights in a regression model to adjust for participant characteristics that differ between the groups.

The incidence of ID or IDA will be examined among participants in the control group (who are not ID and do not have IDA at baseline by definition). These estimates will be in the form of events per unit time. If someone is found to be ID or IDA and then resolves that person re-enters the risk pool for an event. To account for multiple events in the same individual, the generalized estimating equation version of Poisson regression will be used with the robust standard error if necessary. The same approach will be used to examine the incidence of ID and IDA separately.

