### 2.2 Randomization

There is no randomization in the cross-sectional component. In the parallel groups' component, the 2 groups will be determined based on the need for iron supplementation, so the treatment is not assigned by randomization.

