- Vegetarian status (No, Strict, or Partial).

History of Blood Loss:

- Ever given medicine for the treatment of malaria (Yes or No).
- Given medicine for the treatment of malaria within the last 3 months (Yes or No).
- Bleeding piles in the last 3 months (Yes or No).
- Stomach ulcer in the last 3 months (Yes or No).
- Bled from an injury in the last 3 months (Yes or No).
- Surgery in the last 3 months (Yes or No).
- Currently on NSAID painkillers (Yes or No).
- Have sibling(s) with known repeated anaemia (Yes or No).

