### Secondary analyses of secondary outcomes related to safety and feasibility

To maximize the power to detect an association between group membership and safety outcomes, a composite of grade 3 and 4 AEs, SAEs, gastro-intestinal problems, malaria, and bacterial infections will be constructed and compared between the groups.

The frequency of this composite will be compared between groups using Fisher's exact test. Furthermore, logistic regression models will be fit with group membership, sex, and age as covariates and the odds ratio associated with group membership will be estimated along with a 95% confidence interval. These models will be parameterized so that an OR greater than 1 indicates that the intervention group has a higher incidence of negative outcomes. Components of the composite will also be investigated using a similar approach.

The questions about known side effects to iron supplementation ask: Has the participant experienced any of the following since the last visit (mark all that apply)?

- Unpleasant taste.
- Constipation.
- Dark tools.
- Nausea.
- Vomiting.
- Abdominal pain.
- Diarrhea.
- Other; specify.

The incidence of each of these outcomes over follow-up will be computed and logistic regression models will examine the impact of group membership, sex, and age on these outcomes. The odds ratio and a 95% confidence interval for the group membership variable will be used to summarize the association. Models which look at the incidence of any of these outcomes will also be examined and an odds ratio and 95% confidence interval will be used to summarize the relationship.

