#### 7.2.3 Sensitivity analyses

In the primary analysis, individuals are excluded if they did not receive iron supplementation at enrolment but received it during follow-up due to changes in ferritin or haemoglobin values. Sensitivity analyses will be conducted for the primary outcome by including those requiring iron supplementation during follow-up in the control group.

Since the treatment is not assigned at random there is a strong potential that confounders will introduce bias into the estimates of the treatment effects. As an attempt to remedy this, sensitivity analyses using inverse probability weighting will be conducted for the primary outcome and the secondary outcomes that relate to efficacy. If we use  $X_i$  to represent group membership for participant  $i$  and  $Z_i$  is a vector of predictors for this participant, the first step of the analysis is to estimate the stabilized inverse probability of "treatment" weights  $W_i$  for subject  $i$ ,  $W_i = P(X_i = x_i)/P(X_i = x_i|Z_i)$ . The predictors  $Z_i$  include age, sex, screening haemoglobin concentration, screening plasma ferritin concentration, socio-economic status, medical history, and diet. An estimate of  $P(X_i = x_i|Z_i)$  can be obtained by logistic regression

and  $P(X_i = x_i)$  can be estimated by the sample proportion. One then uses these weights in a regression model to adjust for participant characteristics that differ between the groups.

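### Safety comparisons between the non-randomised arms are open to confounding: they adjust for sex and age only, and the SAP leaves them out of the confounding analysis that the Protocol states without that limit

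*SAP*

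**What the plan says.** SAP 2.2 says that the groups are formed by need for iron, "so the treatment is not assigned by randomization". SAP 1.2 (Design) gives the rule: iron deficiency, iron deficiency anaemia or sex-specific low haemoglobin puts a participant in the iron arm, and everyone else is a control.

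For the safety composite, SAP 7.2.2 states: "The frequency of this composite will be compared between groups using Fisher's exact test". It adds that "logistic regression models will be fit with group membership, sex, and age as covariates", with a similar approach for the components. For the listed side effects of iron, "logistic regression models will examine the impact of group membership, sex, and age on these outcomes".

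Under History of Blood Loss, SAP 3.4 lists among the baseline items "Given medicine for the treatment of malaria within the last 3 months (Yes or No" and "Currently on NSAID painkillers (Yes or No", together with bleeding piles and stomach ulcer in the last 3 months.

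On confounding, the Protocol's Quantitative Data Analysis section warns: "Since the treatment is not assigned at random there is a strong potential that confounders will introduce bias into the estimates of the treatment effects". It proposes inverse probability weighting as a remedy, with no restriction on outcomes, in the paragraph that directly follows its safety analyses. SAP 7.2.3 repeats the warning but narrows the remedy: "sensitivity analyses using inverse probability weighting will be conducted for the primary outcome and the secondary outcomes that relate to efficacy".

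**The concern.** Safety is not a side issue here. Under Acceptability, both documents make the safety profile of iron part of the primary objective, to be established against a similar group without iron. The allocation rule works against that similarity. The SAP itself files ulcer, piles, NSAID use and malaria treatment under blood loss, and the Protocol's introduction names loss of iron as a major cause of iron deficiency. These items could therefore be more common in the iron arm. Ulcer and NSAID use could plausibly also predict abdominal pain, nausea and vomiting, and recent malaria treatment could mark continuing exposure to malaria. Gastrointestinal problems and malaria are both components of the composite.

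If the arms differ on these items, a sex-and-age odds ratio mixes the difference in history with any association with iron. The pilot informs the UH3 phase, so a misread signal, or a missed one, could carry forward.

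**Working it through.** **1. Is the gap there?** Setting the sections side by side:

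| Element | Primary and efficacy outcomes | Safety outcomes |
|---|---|---|
| Main models (SAP 7.2.1, 7.2.2) | group, sex, age, screening haemoglobin; ferritin added for the secondary outcomes | group, sex, age; Fisher test unadjusted |
| Weighting, Protocol | stated without limit | stated without limit, directly after the safety analyses |
| Weighting, SAP 7.2.3 | yes | not included |
| Blood-loss history items (SAP 3.4) | not named among the weighting predictors | in no safety model |

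The gap is there, and the SAP is narrower than the Protocol without giving a reason.

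**2. The plan's own figure.** The documents give no event rate or power for safety. The only sample size is for haemoglobin: n = 2(1.960 + 1.036)² × 1.89² / (1.0 − 0.3)² = 130.9, so 131 per arm, and 262/0.9 = 291.1, rounded up to 292. This reproduces the plan. It bears on the present point only by fixing the scale at 131 per arm.

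**3. How large could the distortion be?** The documents give neither the prevalence of the history items nor safety event rates, so these inputs are assumptions:
- no effect of iron;
- event risk b = 0.15 without the history factor;
- the factor multiplies the odds by g = 2 to 4;
- prevalence q₁ in the iron arm and q₀ in controls.

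Risk with the factor: r = gω/(1 + gω), with ω = 0.15/0.85 = 0.1765. For g = 2, r = 0.261; for g = 4, r = 0.414.

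Risk in an arm: q·r + (1 − q)·0.15. The spurious odds ratio compares the two arms. At 20% v 10% and g = 2, the risks are 0.2 × 0.261 + 0.8 × 0.15 = 0.172 and 0.1 × 0.261 + 0.9 × 0.15 = 0.161, so the odds ratio is (0.172/0.828)/(0.161/0.839) = 1.08.

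Fisher rejection is the exact probability that the two-sided test at 5% is significant with 131 per arm.

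| Prevalence, iron v control | Spurious OR, g = 2 to 4 | Fisher rejection |
|---|---|---|
| equal (both 0%) | 1.00 | 3.4% |
| 10% v 5% | 1.04 to 1.10 | 3.5 to 4.2% |
| 20% v 10% | 1.08 to 1.19 | 4.0 to 6.3% |
| 30% v 15% | 1.12 to 1.27 | 4.6 to 9.6% |
| 40% v 15% | 1.21 to 1.47 | 6.7 to 20.8% |

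With the imbalance reversed, the odds ratios invert: 10% v 20% gives 0.84 to 0.92.

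**4. Sampling error for scale.** At 15% risk in both arms, SE(log OR) = √[2(1/(131 × 0.15) + 1/(131 × 0.85))] = 0.346. The 95% interval multiplies or divides the odds ratio by exp(1.96 × 0.346) = 1.97.

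**5. Room for extra covariates.** At event risks of 5%, 10% and 20%, 262 participants yield about 13, 26 and 52 events. A gastrointestinal model with group, sex, age, ulcer, NSAID use and piles has six slopes, so about 2, 4 and 9 events per slope. A malaria/infection model with recent malaria treatment added has four slopes, so about 3, 6.5 and 13.

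**The case against.** The strongest reply is that a risk of confounding is not a finding of confounding. Neither document gives the frequency of any history item by arm, so even the direction is unknown.

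Eligibility also works against large imbalances. Participants must pass the donor questionnaire, which asks about stomach ulcer and current medication. A positive malaria test or helminthic infection at screening excludes from the trial. A prevalence of 20 to 40% for ulcer or NSAID use is hard to reconcile with that. In the milder scenarios the distortion is small beside an interval spanning about a factor of two either way. The SAP mostly speaks of associations when it describes the safety odds ratios, and with few events extra covariates are costly.

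Most of this stands, and it rules out several stronger readings:
- A reader might infer that the gastrointestinal and malaria results will be confounded, or that any excess would be wrongly put down to iron. The documents support only that the comparison is unprotected.
- A reader might take 21% as the expected false-signal rate. It needs 40% v 15% prevalence and a conditional odds ratio of 4 together.
- A reader might infer that no planned analysis could adjust safety for these factors. The Protocol's weighting has no outcome limit and an unspecified predictor vector, so it could; it is the SAP that leaves safety out.

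The reply does not remove the point. The malaria exclusion concerns infection at screening, not treatment in the previous 3 months, and piles and recent malaria treatment are less covered by screening than ulcer. The SAP still plans to summarise all four items at baseline.

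**Conclusion.** The point holds as a gap in the plan, not as a demonstrated bias. Safety is compared between arms formed by iron status and haemoglobin, with adjustment for sex and age at most, and the SAP drops safety from an analysis that the Protocol states without limit. Relevant history is collected and goes unused in the safety models.

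Under the assumptions shown, the likely size is modest: a spurious odds ratio of about 1.1 to 1.2, with rejection of 4 to 6% against 3.4%, at 20% v 10% prevalence. The extreme case at 40% v 15% reaches 1.47 and 21%. For ulcer and medication the lower end is more plausible because of donor screening. All of these figures rest on assumed prevalences, base risk and strength of association, on one binary factor, and on 131 per arm. A reversed imbalance would hide an excess instead of creating one.

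The change is worth making because safety belongs to the primary objective and the data are already collected. Because events may be few, it should support the planned model, not replace it.

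**What to change.** Extend SAP 7.2.3 to the safety composite, the gastrointestinal outcomes and the malaria/infection outcomes:
- Use a propensity score or a Firth logistic model with sex, age and the collected history: recent malaria treatment for malaria/infection; ulcer, NSAID use and piles for gastrointestinal outcomes; these items together for the composite.
- Leave out screening haemoglobin and ferritin. With sex, they define the arms, so carrying over the predictor list of SAP 7.2.3 unchanged would break positivity and give unstable weights. That list also does not name the blood-loss items.
- Keep the Fisher test and the sex-and-age model as planned, report the sex-and-age and extended results side by side, and describe the odds ratios as associations.
- Align the SAP with the Protocol on which outcomes the confounding analysis covers.

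The cost is SAP wording and one further set of models, with no new data. Intervals will be wider when events are few, and if screening makes an item rare its coefficient will be poorly estimated. The change gives no protection against reporting bias: participants and investigators are unblinded, and adjustment for history does not touch that.

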Participants will be followed up every 2 months and will be interviewed by members of the research team and appropriate CRFs completed by study staff. Adherence to iron supplementation and nutritional counseling will be assessed biweekly by phone and at each visit.

Participants with suspected adverse events of iron supplementation will be appropriately managed. Participants with suspected bacterial infections will be assessed with blood cultures (if indicated) and tested for malaria parasites during study visits. Malaria preventive measures will be discussed with all study participants on enrolment, and they will be encouraged to use these preventive measures throughout the study. A history of medical events and selected potential adverse events will be obtained at each scheduled visit and during biweekly follow up phone calls. Participants will also be given identification cards to carry with them at all times providing instructions directed to any health care provider who sees them for an unscheduled medical care visit.

- ***Treatment***

The planned duration of treatment is 4 months. Participants with a low plasma ferritin <15 μ g/L, with or without anaemia, will be given oral iron supplementation and nutritional counseling. Treatment will continue for 16 weeks or until the end of follow-up, during which participants will be followed up for adherence counseling at each visit. Clear written instructions for use 3 times a week will be discussed with them. Research staff will contact participants every 2 weeks by phone for adherence and feedback, and to remind participants to keep their scheduled study visits.

Testing of plasma ferritin and FBC after 4 months of supplementation will allow us to assess for response to study treatment with regards to iron stores. After correction of iron depletion or IDA, FBC and plasma ferritin will be monitored at 4 months from baseline. Participants after the end of the intervention phase still found to be iron deficient or anaemic will continue management and further evaluation at the haematology clinic.

- **Discontinuation**

If discontinuation of study treatment occurs, the investigator should make a reasonable effort to understand the primary reason for the participant's premature discontinuation of study treatment and record this information.

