Schedule for Data Collection and Reporting of Specific Events

Safety assessments will consist of monitoring and recording all AEs related to iron supplementation. It will also include regular monitoring of laboratory assessments including FBC and plasma ferritin.

Steps to limit adverse events due to iron supplementation:

All study participants will be evaluated at each visit as well as during an acute event. Malaria preventive measures will be discussed with all study participants on enrolment, and they will be encouraged to use these preventive measures throughout the study. A history of medical events and potential adverse events will be obtained at each visit. Participants will also be given a card to carry with them at all times providing instructions directed (including contact number of PIs) to any health care provider who sees them for an unscheduled medical care visit. Treatment will be given to those with signs and symptoms suggestive of an adverse event. They will be monitored with a FBC, cultures will be done if bacterial infection suspected and tests for malaria parasites will be done.

Iron supplementation with nutritional counseling for potential blood donors will be given for 4 months (16 weeks). Nutritional counseling for all study subjects receiving iron supplementation will be done at each visit including the need for participants to eat before taking study treatment to help minimize gastrointestinal effects. Participants will also be counseled on potential iron-food interactions and how to minimize that from occurring. A consumer-friendly brochure on safe use of medicines including food interactions and medicine interactions involving iron will be provided to participants.

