## **Objectives**

### **Primary Objectives**

The primary objective of the Iron Supplementation Trial is to determine the potential for an iron supplementation strategy to increase blood donations in Ghana. To determine this potential, the study will investigate the feasibility and acceptability of this intervention along with key return blood donation measures among first-time blood donors found to have low haemoglobin or found to have IDA or be ID within the catchment areas of the SZBC. These aspects of the potential for this intervention will be

operationalized as follows:

- **Feasibility** of recruitment, enrolment, retention, and adherence will be evaluated with a target retention rate > 90% of all participants recruited completing the trial. If we are unable to achieve this target, alternative strategies will be considered for the UH3 phase.
- **Acceptability** will involve establishing the safety profile of 3 times weekly low dose ferrous sulphate (65mg elemental iron) supplements among those assigned to iron supplementation at enrolment. This safety profile will be established by comparison to a similar group of participants who do not receive iron supplementation. Participant and key informant views and perspectives of barriers and recommendations for using iron supplementation and nutritional counselling to increase the blood donor pool will also be investigated with participant questionnaires. In addition, FGDs and key informant interviews will provide critical insights into the acceptability of this intervention.
- **Key blood donation measures** include haemoglobin levels at 4 months, the change in haemoglobin concentration, ferritin levels at 4 months, the proportion of participants with corrected ID, the proportion of participants who return to the blood centre to donate blood and the proportion of returners who are able to successfully donate (not deferred). In addition, the incidence of ID and IDA among blood donors will be determined among those who consent to the Iron Supplementation Trial at screening.

To achieve this objective, a pilot parallel groups trial will be conducted for one year. This allows for enrolment over a maximum of 6 months and 6 months of follow-up for the last individual enrolled. The follow-up period incorporates 4 months of the iron supplementation intervention.

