## 4 Administration of Study Treatment

Potential first-time donors will be asked if they are interested in participating in a study of the prevalence of ID and IDA and the impact of iron supplementation on haemoglobin levels and repeat donation. Those who express interest, consent to the study, and are eligible will be asked to return within 3 weeks. During this 3-week period a FBC, a peripheral blood film analysis, and a plasma ferritin measurement will be conducted, and participants will be classified as iron supplement participants (e.g., anaemic, ID, IDA) or otherwise (which we refer to as controls in this protocol).

Those found to be anaemic, ID or IDA will receive oral iron supplementation and nutritional counselling. The oral iron supplements will be ferrous sulphate 200mg (65mg Elemental iron). The iron supplements are already available at the Korle-Bu Teaching Hospital Pharmacy. The study principal investigators and study pharmacist will ensure the medicine is stored properly and dispensed only when needed for study participants. The following will be monitored and completed on a periodic basis to ensure the medicine is within study guidelines, pharmaceutical compliance, and manufacturer guidelines:

Drug Accountability Record.

Iron supplement Safety and Handling Sheet.

Controls will not be given iron supplementation at enrolment but will receive the standard practice of nutritional counselling for blood donors. If someone not given iron supplements at enrolment is found to be anaemic, ID or IDA at a follow-up visit that individual will receive iron supplements.

All study participants will have nutritional counselling, dietary advice, and for those

receiving iron, the need for iron therapy to be used consistently 3 days a week.

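### SAP 7.2.2 has no safety comparison limited to the planned 16-week iron course; one Day 0 to Interim Visit 2 table beside the 24-week comparison would supply it (minor)

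*SAP*

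**What the plan says.** **Side-effect items.** SAP 7.2.2 (secondary analyses of safety and feasibility outcomes) asks at each visit: "Has the participant experienced any of the following since the last visit". It then says "The incidence of each of these outcomes over follow-up will be computed" and fits logistic models with group, sex and age. Follow-up is 6 months, and the schedule in SAP Appendix A has adverse events assessed up to the Final Visit at week 24.

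**Safety composite.** "The frequency of this composite will be compared between groups" by Fisher's exact test, with a logistic model beside it. Neither the SAP nor the Protocol's Data Analysis section gives a time window. The efficacy outcomes in SAP 7.2.1 and 7.2.2 each carry one (4 or 6 months).

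**Iron course.** The Protocol (steps to limit adverse events) plans 4 months, or 16 weeks, and the SAP objectives agree on 4 months. The Protocol's Treatment paragraph is looser: "Treatment will continue for 16 weeks or until the end of follow-up". It adds: "Participants after the end of the intervention phase still found to be iron deficient or anaemic will continue management" at the haematology clinic.

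**Controls who start iron.** SAP section 4: "If someone not given iron supplements at enrolment is found to be anaemic, ID or IDA at a follow-up visit", that person is given iron. SAP 7.2 fixes the groups by assignment at enrolment. Excluding such controls is stated for the primary outcome (7.2.1) and the efficacy secondary outcomes (7.2.2), but not for safety. The sensitivity analyses in 7.2.3 do not cover safety either.

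**Objective.** On acceptability, the SAP says: "This safety profile will be established by comparison to a similar group of participants who do not receive iron supplementation".

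**The concern.** The only planned safety contrast compares enrolment groups, over 24 weeks for the checklist and over an unstated period for the composite. Part of the iron arm's counted time is planned to be off iron, and some control time may be on iron. If the excess risk exists only while tablets are taken, both features pull the odds ratio towards 1. The pilot is meant to inform the next phase on how well this regimen is tolerated, and no planned figure describes tolerability during the course itself. If the window is left open, it may also be chosen after the data are seen.

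**Working it through.** **1. Figures in the plan.** The documents give no event rate, odds ratio or power for safety, so there is no safety figure to reproduce. The sample size does reproduce: 2 × (1.960 + 1.036)² × 1.89² / (1.0 − 0.3)² = 130.9, so 131 per arm; 262 / 0.9 = 291.1, so 292 in total, or 146 per arm.

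**2. Off-iron share of the iron arm's time.**
- Iron stops at week 16: 8/24 = 33%.
- Iron stops at week 18 (late end of the Interim Visit 2 window): 6/24 = 25%.
- Half the arm continues to week 24: 0.5 × 8/24 = 17%.

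**3. Direction, under one condition.** Let o1 and o0 be the odds of at least one event by week 16 (iron, control). Let s be the chance of a first event in weeks 16 to 24, equal in both arms once iron has stopped. Then OR24 = (o1 + s)/(o0 + s). This is below o1/o0 whenever o1 > o0 and s > 0.

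**4. Illustration (assumed rates).** Background risk is p per 8 weeks, doubled to q = 2p only while on iron, with 146 per arm.
- Iron arm: 24 weeks 1 − (1−q)²(1−p); 16 weeks 1 − (1−q)².
- Control arm: 24 weeks 1 − (1−p)³; 16 weeks 1 − (1−p)².
- It follows that RD24 = (1−p) × RD16, where RD is the risk difference.

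At p = 10%, the risks are 0.424 vs 0.271 over 24 weeks and 0.360 vs 0.190 over 16 weeks.

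| p | OR, 24 vs 16 wk | RD, 24 vs 16 wk | Exact Fisher power (two-sided 5%), 24 vs 16 wk |
|---|---|---|---|
| 1% | 1.69 vs 2.03 | 0.0195 vs 0.0197 | 7% vs 8% |
| 2% | 1.72 vs 2.06 | 0.038 vs 0.039 | 17% vs 21% |
| 5% | 1.80 vs 2.17 | 0.088 vs 0.093 | 43% vs 56% |
| 10% | 1.98 vs 2.40 | 0.153 vs 0.170 | 75% vs 88% |

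With 131 per arm (after the planned 10% loss), power at p = 10% is 70% vs 85%.

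**5. What changes the answer (p = 10%).**
- 10% of controls start iron at Interim Visit 1: the 24-week control risk is 0.9 × 0.271 + 0.1 × [1 − 0.9 × 0.8²] = 0.286, giving OR 1.84 and RD 0.138.
- Half the iron arm continues to week 24: risk 0.5 × 0.424 + 0.5 × 0.488 = 0.456, giving OR 2.25.
- Doubled risk persists to week 24: OR 2.56, power 96%. The 24-week analysis is then the stronger one (96% vs 88%).
- Control events recorded only about 85% as fully as iron-arm events: the 24-week OR returns to 2.40. At 80% it is 2.59.

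**6. The added window (p = 10%).**
- If Interim Visit 2 falls at week 18 and iron stopped at week 16, 2/18 = 11% of the window is off iron; OR is 2.26 and RD 0.166.
- With 10% of controls on iron from Interim Visit 1, the table by enrolment group has control risk 0.9 × 0.190 + 0.1 × 0.280 = 0.199 and OR 2.26.
- Leaving out those controls' events after iron start gives 0.9 × 0.190 + 0.1 × 0.100 = 0.181 and OR (0.360/0.640)/(0.181/0.819) = 2.55, because their observed time is cut short.
- Under these assumptions the two tables lie either side of the no-crossover value of 2.40, so both should be shown.

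**The case against.** The strongest defence is that the planned analysis is a coherent estimand. The sentence of the objective just before the one quoted defines the safety profile among those assigned iron at enrolment, sets no 16-week limit, and matches the grouping in SAP 7.2. Counting all follow-up also catches late malaria or bacterial infection. This stands: a reader might infer that the plan contradicts its own objective, and the text does not support that. What is missing is a second, complementary comparison.

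A reader might also infer that the reported odds ratio will understate harm. The documents do not establish this. Dilution needs risk to be raised only on iron, and other features can push the other way: groups are not randomised (SAP 7.2.3), nobody is blinded (SAP 2.3), and only AEs possibly related to iron are recorded (SAP 5). Step 5 shows that modest under-recording in controls cancels the dilution. The shorter window carries the same biases.

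Third, the Protocol expects AEs to be infrequent. At p = 1% the approximate 95% intervals are 0.50 to 5.70 around 1.69 and 0.49 to 8.47 around 2.03, so sampling error swamps the shift. This stands for SAEs, grade 3 or 4 AEs and infections. It has less force for checklist items such as dark stools or constipation, which may be common.

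Last, the Treatment paragraph leaves the iron duration open, so the 25% to 33% off-iron share is the planned figure and may turn out lower. That is a reason to report iron use after Interim Visit 2.

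**Conclusion.** The point holds as a minor gap. SAP 7.2.2 plans no safety comparison confined to the iron course, leaves the composite's window unstated, and counts controls who start iron as controls for safety. If iron raises risk only while taken, the odds ratio is diluted: 1.98 against 2.40 at an assumed 10% background risk per 8 weeks, and 1.69 against 2.03 at 1%. The practical effect is confined to common checklist and gastrointestinal items; for rare events power and the risk difference are essentially unchanged. All rates are assumptions, since the documents give none. No net direction of bias is claimed, and the haemoglobin endpoint is unaffected.

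**What to change.** In SAP 7.2.2:

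1. Keep the comparison by enrolment group over all follow-up, and state that its window, for the composite as well, is Day 0 to week 24.
2. Add one supplementary table for Day 0 to Interim Visit 2: checklist items, gastrointestinal events and the composite, by enrolment group, with the same Fisher and logistic (sex, age) methods. Give risk differences beside odds ratios.
3. Repeat that table without control events after iron start. Note that this may be informative, because these controls start iron on becoming anaemic or iron deficient, and that it shortens their observed time.
4. Report how many in the iron arm were still taking iron after Interim Visit 2.

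Interval-based GEE or Poisson rate models are optional, and only for items with enough events; they would be unstable for sparse ones.

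**Cost:** SAP wording and one supplementary table with its repeat. Checklist answers by visit, AE start dates (as far as possible), iron given to controls and Final Visit adherence are already to be collected, and the SAP may be updated until database lock. **Downsides:** fewer events in the shorter window, up to 2 off-iron weeks if Interim Visit 2 falls at week 18, and possibly informative censoring of controls.
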